MBSR condition: MBSR is a standardized protocol consisting of 8-weekly 2.5 hour sessions, homework consisting of 30-45 minutes of mindfulness meditation practice six days per week and a one-time half-day (4-6 hour) retreat. This will be offered at the Social Gerontology and Health lab, [name] Our MBSR intervention is based upon the standard regimen taught at the University of Massachusetts.(Kabat-Zinn, 2013) Participants will attend weekly group sessions at the Yale Stress Center at the Yale School of Medicine taught by an experienced MBSR instructor ([name] MA MSW) who collaborates closely with Co-I [name]. Each weekly session will consist of an instructor-led mindfulness meditation, followed by a discussion of the meditation and its application into participants' everyday life. Formal meditations that will be led and discussed include eating meditation, body scan, sitting meditation, Hatha Yoga, and walking meditation. Participants will take their partners blood pressure reading with an automated Carescae cuff at each MSBR class. In addition, informal mindfulness practices of awareness of pleasant and unpleasant events and awareness of routine events will be discussed. Participants will be recording their daily mindfulness practice minutes on attached form.

Wait list condition: After the MBSR condition groups have completed their sessions, the participants in the Wait List group may choose to participate in the 8-week MBSR class. Participants will be provided with a coupon to participate starting July 2018. In the meantime, participants in the Wait list group will complete the same measures at the same time points as participants enrolled in Cohort 1 and Cohort 2 of the MBSR conditions.

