The baseline, 8-week, and 3-month visits will entail data collection using validated questionnaires and self-report paper forms at the CSRU. The eight week visit will take place between five to eleven weeks after enrollment. The three month visit will occur from 10 to 14 weeks after enrollment. At the 8-week visit participants will be asked to complete a qualitative interview in addition to the paper surveys. Responses will be recorded on a cell phone and we will use transcription plus LLC <https://www.transcriptionplus.net> transcription services. Participants will complete the forms themselves, and they will be entered into the OnCore system by the project manager. These forms will be kept in paper form in each study participant's record and will be kept in a locked file cabinet at the Yale Center for Clinical Investigation. Only the PI and project manager will have access to the participant's records. Forms will be coded with subject number; no personally identifiable information will be associated with these forms. Blood will be drawn by staff at the Church Street Research Unit and sent to the YCCI Core Lab for processing of the glucose, cholesterol, and triglyceride markers. The biomarker information will then be linked to our study on OnCore. The OnCore database will be supported by the Yale Center for Clinical Investigation/ CTSA. Incomplete or missing data prompts follow-up calls or electronic queries in OnCore. Our OnCore database will be checked for completeness in real-time from internal checks; while the PI and project manager will perform weekly audits for complete data.

The project manager will use a study cell phone for the purposes of recruitment, and reminder texts for participants. The project manager will make routine follow-up calls to remind study subjects of their appointments. Attrition will be minimized and data collection optimized with a relatively short intervention duration together with a \$150 individual participant remuneration. Payment will be made through the ONCORE bank of America gift card program with remuneration to be as follows. (\$50 dollars at baseline, \$50 dollars at eight week follow-up and \$50 dollars at three month follow-up) In [name] ongoing studies in fibromyalgia and Irritable Bowel Syndrome patients (n=108), he has achieved complete (no missing data) datasets based on robust data collection, retention, and follow-up procedures in collaboration with the YCCI.

Timeline.

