--	--	--	--	--	--	--	--	--	--	--	--	--	--	--	--	--	--	--	--

(BP): $\geq 130/85$ mm Hg and/or taking BP medication; (e) High fasting glucose: ≥ 110 mg/dL (≥ 6.1 mmol/L).

Exclusion criteria. Non-English speaking, practicing mind–body therapies more than once/week (e.g., meditation, yoga), taking psychiatric medications, substance abusers, persons with suicidal ideation, or severe psychopathology.

8. How will **eligibility** be determined, and by whom?

Preliminary eligibility will be determined by the Project Manager based on responses to questions on telephone screening. Final eligibility will be determined by [name] based on corroborating the diagnosis of metabolic syndrome from their medical chart.

9. Risks:

Mindfulness-based stress reduction has been studied in a number of clinical trials for many conditions. There are no known side effects of mindfulness-based stress reduction. There are potential risks of increased symptoms because mindfulness training can increase awareness of body sensations. As the mindfulness-based stress reduction program incorporates yoga, there is also a risk of physical injury, such as pulled or strained muscles. There are theoretical risks of meditation programs including increased psychological distress in persons with unstable psychological conditions or that are suicidal. However, persons with these conditions will not be allowed to participate in this study.

Other risks from participating in the study include the breach of confidentiality about subject's health status and participation in the study. This is very unlikely to occur, as all study investigators are trained and certified in research privacy.

The risks involved in drawing blood from a vein may include, but are not limited to, momentary discomfort at the site of the blood draw, possible bruising, redness, and swelling around the site, bleeding at the site, feeling of lightheadedness when the blood is drawn, and rarely, an infection at the site of the blood draw. There are no major risks associated with these procedures.

There is a risk of breach of confidentiality.

Dobkin notes possible risks noted in other types of meditation programs including increases in anxiety, panic, tension, less motivation in life, boredom, pain, impaired reality testing, confusion and disorientation, feeling 'spaced out', depression, increased negativity, being more judgmental and feeling 'addicted to meditation.' (Dobkin, Irving, & Amar, 2012)

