Safety and tolerability will be assessed through participant self-report of symptoms or changes in symptoms since baseline (obtained from adverse event logs and direct query at the sessions and at the 8 week and 3 month follow up visits) until completion of the study. Comparison of tabulated safety events by grade (mild, moderate, severe) between intervention and control groups will help identify any unforeseen consequences of the treatment regimen. Based on the safety profile of MBSR, there is minimal risk of adverse events. Should any subjects experience adverse effects related to the intervention, these will be reported using a standard form to the Yale Human Research Protection Program. All subjects will have direct (phone and email) access to the Principal Investigator. If any adverse events occur requiring immediate medical attention, the PI will guide and advise subjects in the medical management of acute and/or emergent reactions. In most cases, this will entail calling '911' and an immediate emergency department referral.

In recent systematic reviews of MBSR for a variety of conditions, no adverse effects were reported (Cramer, Haller, Lauche, & Dobos, 2012; Katterman, Kleinman, Hood, Nackers, & Corsica, 2014). There are, however, theoretical risks of MBSR, including increased symptomology resulting from awareness training (Fjorback, Arendt, Ornbol, Fink, & Walach, 2011), as well as using mindfulness interventions instead of more effective treatments (Marchand, 2013).

Dobkin notes possible risks noted in other types of meditation programs including increases in anxiety, panic, tension, less motivation in life, boredom, pain, impaired reality testing, confusion and disorientation, feeling 'spaced out', depression, increased negativity, being more judgmental and feeling 'addicted to meditation.' (Dobkin, Irving, & Amar, 2012)

Dobkin also notes a case report where mania was precipitated by meditation as well as transient meditation-induced psychosis (Dobkin et al., 2012). Our MBSR teacher ([name]) notes contraindications in active substance abusers, persons with suicidal ideation, or severe

psychopathology.

Data and Safety Monitoring Plan:

11. **Data and Safety Monitoring Plan:** Include an appropriate Data and Safety Monitoring Plan (DSMP) based on the investigator's risk assessment stated below. (Note: the HIC will make the final determination of the risk to subjects.)

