- a. What is the investigator's assessment of the overall risk level for subjects participating in this study? Minimal risk
 - b. If children are involved, what is the investigator's assessment of the overall risk level for the children participating in this study? n/s
 - c. Include an appropriate Data and Safety Monitoring Plan. Examples of DSMPs are available here <http://your.yale.edu/policies-procedures/forms/420-fr-01-data-and-safety-monitoring-plans-templates> for
 - i. Minimal risk
 - ii. Greater than minimal

12.

The principal investigator is responsible for monitoring the data, assuring protocol compliance, and conducting the safety reviews at the specified frequency [*monthly*]. During the review process the principal investigator will evaluate whether the study should continue unchanged, require modification/amendment, or close to enrollment.

The principal investigator and the Institutional Review Board (IRB) have the authority to stop or suspend the study or require modifications.

This protocol presents minimal risks to the subjects and Unanticipated Problems Involving Risks to Subjects or Others (UPIRSOs), including adverse events, are not anticipated. In the unlikely event that such events occur, Reportable Events (which are events that are serious or life-threatening and unanticipated (or anticipated but occurring with a greater frequency than expected) and possibly, probably, or definitely related) or Unanticipated Problems Involving Risks to Subjects or Others that may require a temporary or permanent interruption of study activities will be reported immediately (if possible), followed by a written report within 5 calendar days of the Principal Investigator becoming aware of the event to the IRB (using the appropriate forms from the website) and any appropriate funding and regulatory agencies. The investigator will apprise fellow investigators and study personnel of all UPIRSOs and adverse events that occur during the conduct of this research project through regular study meetings and via email as they are reviewed by the principal investigator.

13. **Statistical Considerations:** Describe the statistical analyses that support the study design.

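### Adverse events are asked about at MBSR classes that only one arm attends, yet the arms are compared on the resulting table, so minor events will probably look more frequent under MBSR

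*Protocol*

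**What the plan says.** Section I, item 10 of the protocol (Protections against risk) assesses safety and tolerability by participant self-report of symptoms since baseline, "obtained from adverse event logs and direct query at the sessions and at the 8 week and 3 month follow up visits". The next sentence sets out a "Comparison of tabulated safety events by grade (mild, moderate, severe) between intervention and control groups", intended to reveal unforeseen effects of the intervention. It does not limit that comparison to sources available in both arms.

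Section I, item 3 shows who attends sessions. Under the MBSR condition, "MBSR is a standardized protocol consisting of 8-weekly 2.5 hour sessions", with a one-time half-day retreat in addition. Under the wait-list condition, "After the MBSR condition groups have completed their sessions, the participants in the Wait List group may choose to participate" in the class, by coupon from July 2018. Until then they complete the same measures at the same time points as the MBSR cohorts. No weekly contact that asks about symptoms is described for them, and the reminder calls concern appointments.

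Some channels are open to both arms. The adverse event logs are not restricted to one arm, and "All subjects will have direct (phone and email) access to the Principal Investigator".

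**The concern.** One arm has a detection channel that the other lacks, and the two arms' records are then set side by side. If the true rates are equal, an extra channel can add records only to the arm that has it. The events most exposed to this are minor and short-lived ones, such as a strained muscle or a passing increase in symptoms. Item 9 foresees both kinds. Such events may be forgotten, or not volunteered, by the 8-week visit, which falls 5 to 11 weeks after enrollment. Before that visit the wait-list arm has no scheduled direct query at all.

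A reader of the table could not separate an effect of MBSR from an effect of asking more often. The likely error is to report excess minor harm that is partly or wholly an artefact of questioning.

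**Working it through.** The plan gives no figure for this comparison, so there is none to reproduce. The check is a count of contacts from the text, followed by an illustration on stated assumptions.

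**Scheduled direct queries per participant** (item 3 and item 10):

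- MBSR: 8 weekly sessions + 2 visits = 10, or 11 if the retreat counts as a session.
- Wait list: 2 visits.

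These are scheduled maxima. They assume full attendance and a query at every session.

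**Effect on recorded events in the class period.** Let v be the probability that channels open to both arms (logs, phone, email, visits) capture a minor event. Let s be the probability that a session captures one they would miss. Neither is in the protocol; both are assumptions. With equal true rates, the wait-list arm records a fraction v and the MBSR arm records v + (1 − v)s. The ratio is

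R = [v + (1 − v)s] / v = 1 + s(1 − v)/v.

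The counts below assume 16 true minor events per arm.

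| v | s | R | MBSR records | Wait-list records |
|---|---|---|---|---|
| 0.9 | 0.5 | 1 + 0.5 × 0.1/0.9 = 1.06 | 16 × 0.95 = 15.2 | 16 × 0.9 = 14.4 |
| 0.5 | 0.7 | 1 + 0.7 × 0.5/0.5 = 1.70 | 16 × 0.85 = 13.6 | 16 × 0.5 = 8.0 |
| 0.3 | 0.9 | 1 + 0.9 × 0.7/0.3 = 3.10 | 16 × 0.93 = 14.9 | 16 × 0.3 = 4.8 |
| 1 | any | 1.00 | 16 | 16 |

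For v from 0.3 to 0.9 and s from 0.5 to 0.9, R therefore runs from 1.06 to 3.10. R is also 1 if s = 0. The ratio does not depend on the number of true events.

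**Effect over the whole follow-up.** Item 3 states: "The three month visit will occur from 10 to 14 weeks after enrollment". Assume a constant true rate, equal capture outside the class weeks, and all 8 class weeks falling before the 3-month visit. The ratio over T weeks is then 1 + (8/T)(R − 1):

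- T = 10: 1 + 0.8 × 0.056 = 1.04, up to 1 + 0.8 × 2.10 = 2.68.
- T = 14: 1 + 0.571 × 0.056 = 1.03, up to 1 + 0.571 × 2.10 = 2.20.

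The protocol does not give the class start date relative to enrollment, so the dilution is approximate.

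**The case against.** The strongest case on the other side has four parts.

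- **This belongs in an analysis plan.** Which sources enter which safety table is ordinary table-shell detail, and item 10 does not say outright that the sources are pooled. This stands in part. But the protocol itself fixes both the unequal questioning and the comparison. If event source is not recorded at collection, no later plan can restore comparability.
- **The shared channels may be good.** If both arms keep continuous logs, v could be near 1 and the ratio near 1. This is fair: the protocol does not say who keeps the logs. It limits the size of the problem, but the imbalance vanishes only if capture is complete or the sessions add nothing.
- **The table is descriptive.** It carries no test or decision rule, and sensitivity in the exposed arm is desirable for finding harm. Reportable "events that are serious or life-threatening and unanticipated" events that are possibly, probably or definitely related are handled individually under the Data and Safety Monitoring Plan. This stands as a reason to keep the session queries and not to overstate the point. It does not make a comparison on unequal sources interpretable.
- **The ratios are assumptions, and counts this small are noisy.** With simple Poisson error, 13.6 against 8.0 differs by 5.6/√21.6 = 1.2 standard errors, and 15.2 against 14.4 by 0.8/√29.6 = 0.15. This also stands: the figures show direction and possible range only.

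**Conclusion.** The concern holds. Followed as written, the plan asks MBSR participants directly about adverse events on 10 or 11 scheduled occasions and wait-list participants on 2, then compares the arms without regard to source. The direction of the bias follows from the design: towards apparent excess minor harm under MBSR whenever the shared channels miss events that sessions catch. The size is unknown. On the assumed values, the ratio is 1.06 to 3.1 for the class period and about 1.03 to 2.7 to the 3-month visit.

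The conclusion rests on reading sessions as the MBSR classes, the only sessions the protocol describes, and on wait-list couples not attending classes during the comparison. The second point is clear for the 8-week comparison. For the 3-month comparison, the protocol does not say outright that every wait-list visit comes before the July 2018 coupon date.

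The consequence is confined to mild and transient events in the safety table. Severe events are less easily forgotten and are probably little affected, and no efficacy result uses the table. The change should be made, but it does not threaten the trial's main conclusions.

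**What to change.** Keep the session queries for participant safety, and add a field to the event form for how each event came to light (session, visit, log, or contact by the participant). State in the plan that:

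- the between-arm table by grade uses events elicited by the same questions and the same recall period at the 8-week and 3-month visits, with log entries added only if both arms keep logs in the same way;
- events elicited at sessions are listed separately for the MBSR arm, as descriptive information;
- this equalises the questioning but not the underlying awareness or recall.

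The last statement is needed because item 9 itself says: "There are potential risks of increased symptoms because mindfulness training can increase awareness of body sensations". Weekly prompting may also improve recall at the visits. For example, if these effects raise visit capture in the MBSR arm from 0.5 to 0.6 (assumption), the visit-only ratio is still 0.6/0.5 = 1.2.

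The cost is one form field and a few sentences, with no extra visits or staff. The downside is that some mild events, including genuine class-related ones, leave the comparative table, though they remain in the MBSR listing.

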Feasibility outcomes will be observed, recorded, and qualitatively evaluated. Descriptive characteristics of the cohort will be summarized with means and standard deviations and counts and percentages according to intervention group. Although this pilot study will not be powered to test all outcomes for statistical significance, the primary quantitative outcomes are expected to have continuous Gaussian distributions making possible the comparison of intervention and control group results with linear mixed effects regression models that can accommodate the clustering of outcome results within couples. Finally, in anticipation of future studies of the metabolic syndrome outcome,

selected analyses will be conducted to compare the utility of the composite metabolic syndrome outcome and with a version of this outcome yielded by a measurement model in a structural equation modeling context.

Hypothesis 1: Self-reported physical health will be greater on average for participants in the MBSR intervention group compared to a wait-list control group. A multivariable linear mixed effects model will be used to assess whether self-reported physical health is greater in the intervention group than in the control group. A random effect will be used to account for the clustering of outcome values within couples. A pre-specified set of covariates will be entered into the regression model including baseline self-reported physical health and demographics and contextual factors that differ significantly across intervention and control groups. Model goodness of fit will be assessed with residual analysis, influence statistics, and goodness-of-fit statistics.

Hypothesis 2: MBSR will reduce each partner's self-reported stress and increase their mindfulness. The analyses for these two secondary outcomes will proceed according to the same procedures as cited for Hypothesis 1 above.

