How quantitative and qualitative data will be combined to understand outcomes. Qualitative data will be analyzed using Atlas.ti software and themes will be identified regarding partner influence on study experience. Key demographic characteristics and results from quantitative questions regarding decision making in participation and adherence will be entered into the software as coded attributes. Queries will be conducted to investigate the relationships between identified themes and coded attributes. Finally, the results of this qualitative analysis will be used to formulate hypotheses about the meanings and mechanisms underlying the quantitative results for Hypotheses 1 and 2, and especially, for the results of dyadic analyses of couple members' simultaneous engagement in the MBSR intervention.

Power: The sample size procedure in PASS shows that in anticipation of loss-to-follow-up, and with recognition of dependency in results from couples, the effective sample size is estimated to be 70, a reduction of 10 from the enrollment of 80 study participants. Assuming power of 80%, an outcome standard deviation of 10, and equal assignments to the intervention and control groups, this effective sample size will allow for detection of a difference between intervention and control groups mean values for the SF-12 outcome of 6.43 or more at the two-sided level of significance of 0.05. The sample size procedure in PASS was performed.

SECTION III: RECRUITMENT/CONSENT AND ASSENT PROCEDURES

1. Targeted Enrollment: Give the number of subjects: 80 participants

- a. Targeted for enrollment at Yale for this protocol: 80
- b. If this is a multi-site study, give the total number of subjects targeted across all sites: N/A

2. Indicate recruitment methods below. Attach copies of any recruitment materials that will be used.

- | | | |
|---|---|-------------------------------------|
|  Flyers |  Internet/Web Postings |  Radio |
|  Posters |  Mass E-mail Solicitation |  Telephone |
|  Letter |  Departmental/Center Website |  Television |
|  Medical Record Review* |  Departmental/Center Research Boards |  Newspaper |

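### MBSR is taught in classes in one arm only, but the model and the effective sample size allow for dependency within couples alone; if classmates' outcomes are correlated, standard errors are too small

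*Protocol*

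**What the plan says.** Protocol, Section I, item 3 (Research Plan). For the MBSR condition: "Participants will attend weekly group sessions at the Yale Stress Center", led by one instructor, with meditation followed by discussion. The wait-list paragraph has control couples measured at the same time points as "participants enrolled in Cohort 1 and Cohort 2 of the MBSR conditions". They may take the course only after the MBSR groups have finished. The readable text gives no number or size of classes.

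Section I, item 13 (Statistical Considerations), Hypothesis 1, specifies a linear mixed model: "A random effect will be used to account for the clustering of outcome values within couples". Hypothesis 2 follows the same procedures. The additional dyadic model has individual and couple variables and no class level.

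The Power paragraph of item 13 adjusts for expected loss to follow-up and then, "with recognition of dependency in results from couples, the effective sample size is estimated to be 70". "Assuming power of 80%, an outcome standard deviation of 10, and equal assignments to the intervention and control groups", it states a detectable difference between arms in "mean values for the SF-12 outcome of 6.43 or more" "at the two-sided level of significance of 0.05".

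**The concern.** People who share an instructor, a room, discussions and a retreat over eight weeks may end up with more similar outcomes than people who do not. Here that can happen in the MBSR arm only, which makes the design partially nested. A couple random effect captures what two partners share, not what ten or so couples in a class share.

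If such a class effect exists, the mean of the MBSR arm varies more than the model believes. Confidence intervals for the SF-12, stress and mindfulness comparisons are then too narrow, and the detectable difference is too optimistic. A result called significant would carry less weight than its p-value suggests, and later studies planned from these estimates would inherit the false precision.

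**Working it through.** **1. The plan's own figure.** Inputs from the Power paragraph: SD 10, power 80%, two-sided 0.05, equal arms, and "the effective sample size is estimated to be 70, a reduction of 10 from the enrollment of 80 study participants", hence 35 per arm.

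Detectable difference = (1.960 + 0.842) × 10 × √(2/35) = 6.70 (normal approximation), or 6.79 with the t distribution. The stated 6.43 does not reproduce. It corresponds to 38 per arm (normal) or 39 per arm (t). With 35 per arm, power at 6.43 is 76.7% (normal) or 75.5% (t). The base for what follows is therefore 6.70.

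**2. Is there slack in the step from 80 to 70?** Taking effective N = 80 × (1 − loss) / (1 + couple ICC), a value of 70 implies a couple ICC of 0.14 with no loss, 0.03 with 10% loss and 0 with 12.5% loss. Little or nothing is left to absorb a class effect.

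**3. Detectable difference with a class effect.** Assumptions: K equal classes in the MBSR arm, so m = 35/K per class on the effective scale, and class ICC ρ. K = 2 is inferred from the two cohorts; K = 4 is shown as an alternative.

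- MBSR-arm design effect: D = 1 + (m − 1)ρ. The wait-list arm has 1.
- Variance of the arm difference is multiplied by (D + 1)/2.
- Detectable difference = 6.70 × √((D + 1)/2); effective N = 70 / ((D + 1)/2).

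| K | m | ρ | D | (D + 1)/2 | Effective N | Detectable difference |
|---|---|---|---|---|---|---|
| 2 | 17.5 | 0.01 | 1.165 | 1.083 | 64.7 | 6.97 |
| 2 | 17.5 | 0.02 | 1.330 | 1.165 | 60.1 | 7.23 |
| 2 | 17.5 | 0.05 | 1.825 | 1.413 | 49.6 | 7.96 |
| 4 | 8.75 | 0.01 | 1.078 | 1.039 | 67.4 | 6.83 |
| 4 | 8.75 | 0.02 | 1.155 | 1.078 | 65.0 | 6.95 |
| 4 | 8.75 | 0.05 | 1.388 | 1.194 | 58.6 | 7.32 |

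**4. Type I error of the couple-only model.** Simulation: 20 couples per arm, no loss, couple ICC 0.14 or 0.30 (assumed), a class effect in the MBSR arm that the analysis ignores. The test is a t-test on couple means with 38 df, which equals the couple random-intercept model in balanced data.

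| ρ | Two classes | Four classes |
|---|---|---|
| 0 | 4.9-5.0% | 5.0-5.1% |
| 0.01 | 5.7-5.9% | 5.3-5.4% |
| 0.02 | 6.7-6.9% | 5.5-5.8% |
| 0.05 | 9.2-9.8% | 6.8-7.0% |

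**5. Hand check of one cell** (two classes, ρ = 0.05, couple ICC 0.14, total variance 100, class variance taken from the residual).

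- Variance of a couple mean within a class: 14 + 81/2 = 54.5. In the wait-list arm: 14 + 86/2 = 57.
- True variance of the arm difference: 54.5/20 + 5/2 + 57/20 = 8.075, so the true SE is 2.84.
- The pooled couple-only estimate expects 54.5 + 5 × (20/19) × (1/2) = 57.13 in the MBSR arm and 57 in the wait-list arm, average 57.07. Its SE is √(2 × 57.07/20) = 2.39.
- The ratio is 1.19, matching the simulated ratio of 1.189, for which the simulated type I error is 9.7%.

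**The case against.** **The inflation is conditional.** A reader might infer that the type I error certainly exceeds 5%. The protocol does not support that: it gives no class ICC, and at an ICC of zero the couple-only model holds its level. This stands, and the point is worded accordingly.

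**The class count is inferred.** Two cohorts need not mean two classes, and the timeline table did not survive text extraction. This stands too, which is why four classes are shown. The effect is then clearly smaller.

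**Direction.** A reader might infer that the error favours MBSR. It does not. The test is two-sided, an understated standard error inflates both tails, and the treatment estimate is not biased by it.

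**Pilot status and an SAP that is not shown.** Item 13 says the pilot is not powered for every outcome, and feasibility is the first aim. A sensitivity analysis is often left to the SAP. But the protocol itself fixes the dependency structure and the power basis, Aim 2 predicts a significant difference, and the Power paragraph states a 5% test with 80% power. The pilot status lowers the stakes without removing the omission.

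**Shared timing.** Wait-list couples are measured at the same time points as the two cohorts, so calendar effects are largely common to both arms. That is correct, but effects arising inside a class remain in the MBSR arm alone.

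**Conclusion.** The point holds in conditional form and merits correction. The design creates a source of dependency in one arm that neither the Hypothesis 1 and 2 model nor the effective sample size recognises.

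Over assumed class ICCs of 0.01 to 0.05, the nominal 5% test has a type I error of about 6% to 10% with two classes and about 5.3% to 7% with four. At the low end the consequence is slight; at an ICC of 0.05 with two classes it is material. Separately from any class effect, 6.43 does not follow from the stated inputs.

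The figures rest on equal classes, an assumed couple ICC of 0.14 to 0.30 in the simulation, and the normal approximation for the detectable differences. They do not cover an instructor effect: with a single instructor, that effect is inseparable from the treatment.

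**What to change.** 1. State how many classes there will be and their planned size.
2. Keep the couple-only model. Beside it, report the Hypothesis 1 and 2 estimates with standard errors recomputed under a partially nested structure: class ICC fixed at 0.01, 0.02 and 0.05 in the MBSR arm and zero in the wait-list arm. The ICC is fixed rather than estimated because so few classes cannot support a class variance estimate.
3. Restate the detectable difference from 6.70, with the range for the planned number of classes (6.97, 7.23 and 7.96 for two; 6.83, 6.95 and 7.32 for four).

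Randomising within cohort or adding a cohort fixed effect would not serve instead: a cohort term common to both arms does not capture variation that exists in the MBSR arm only.

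The cost is one small sensitivity table and a less favourable stated detectable difference. No participants or visits are added.
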